Our study is a prospective, randomized controlled trial in patients diagnosed with chronic pelvic pain. To make the diagnosis, patients must have non-cyclic pelvic pain for duration greater than 6 months which results in functional disability. This is defined as patient reported limitations in social or occupational functioning. One physician will make the diagnosis from patients evaluated in one treatment facility. Inclusion criteria: women >/= 18 years old who are sexually active or desire to be sexually active, no active infection, diagnosed with non-cyclic chronic pelvic pain, duration of symptoms greater than 6 months, neurologically intact, able to accommodate and tolerate the device, not pregnant and not attempting to achieve pregnancy. Exclusion criteria include pregnancy, currently active in pelvic floor physical therapy, active malignancy, patients unable to contract their pelvic floor secondary to causes such as myelopathy, spinal cord trauma, patients with diabetes, vestibulodynia, vulvodynia, a pacemaker, defibrillator or other implanted neuro-modulatory devices, patients with a hypotonic pelvic floor, or those currently on treatment for pain with topical lidocaine, gabapentin or other medications or injections outside of standard analgesics, and severe psychiatric disorders. We will instruct patients to avoid starting any new medications for the treatment of their pelvic pain during the trial.

We will invite subjects meeting criteria to participate in the study. If subjects are interested, they will review and sign the informed consent. Randomization is based on age, diagnosis, and duration of symptoms. Researchers will collect the patient's demographics and general medical history at the initial visit. This includes relevant past medical history, surgical history, allergies, medicines, and social history. At each visit, we will assess pain, quality of life and sexual function. Pain is assessed using the visual analog scale, quality of life measured by the SF-36, sexual dysfunction measured by the female sexual function and pain medication use by a daily journal. We ask each subject to record the date, each completed session, as well as pain medication usage in a provided daily journal. We will make these assessments at baseline, 4 weeks, 8 weeks and 12 weeks.

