We will record demographics, general medical information, questionnaires, and medication usage (including frequency and doses) using the REDCap database designed by the researcher and hosted by the Cleveland Clinic. REDCap (Research Electronic Data Capture) is a secure, web- based application designed to support data capture for research studies, providing 1) an intuitive interface for validated data entry; 2) audit trails for tracking data manipulation and export procedures; 3) automated export procedures for seamless data downloads to common statistical packages; and 4) procedures for importing data from external sources. The database will be reviewed by a statistician prior to data collection. Only the PI and research co-investigators will have access to the stored information. Only the PI, co-PI's and those responsible for analysis will have rights to export identifiable data. The subject's personal health information will be stored in the secure research database and only limited research personnel have access to this database. Great care will be taken to ensure that confidential health information is stored securely and accessible only to the PI and co-investigators.

RANDOMIZATION

In order to minimize bias in the study, we will stratify subjects based on presence or absence of levator spasm.

STATISTICAL METHODS

Numerical values will summarized by mean and standard deviation when they appear to have a normal distribution; otherwise, they will be summarized by median and interquartile range. Categorical values will be summarized by frequency and percentage. Univariable comparisons between groups will be made using two sample t-tests, Wilcoxon rank sum tests, or Chi-square tests, depending on the level of measurement and data distributions.

STUDY AIM ANALYSIS

- 1. Change in pain score from baseline to 12 weeks will be compared using a two-sample t-test. A multivariable linear regression model may be considered if baseline differences between groups are observed.
- 2. Changes in SF-36 subscores from baseline to 12 weeks will be compared using Wilcoxon rank sum tests.
- 3. Changes in FSFI subscales from baseline to 12 weeks will be compared using Wilcoxon rank

sum tests.

4. Frequency of medication from baseline to 12 weeks may be compared using a poison regression model. Dose of medication will be compared using a Wilcoxon's rank sum test.

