Additional analyses using longitudinal methods, including linear mixed effects models and generalized linear mixed effects models, may be used in subsequent analyses to explore the length of time that elapses before the treatment benefit is observed. In all analyses, statistical significance will be determined by a p-value less than or equal to 0.05. Analyses will be performed using R version 3.1.1 (2014-07-10) statistical software (or a later version).

Two interim analyses are planned for this study, to be conducted at 25% recruitment and 50% recruitment. These analyses will be conducted using significance levels of 0.017 and 0.033, respectively. A stopping rule will be applied of any statistically significant increase in pain from baseline as reported on the visual analog scale. The percentage of patients dropping out from the study will also be monitored, with a significantly higher percentage of electrical stimulation patients dropping out being considered a potential safety issue.

POWER ANALYSIS

The researcher currently estimates typical reported pain from this population of patients to be between 8 and 9 on a 10 point scale. A clinically meaningful improvement would be a 30% reduction in reported pain. For the purposes of the power analysis, we assume that the placebo effect of the sham treatment may reduce reported pain by 10%. We assign the mean baseline pain value of 8.5 to each group with a standard deviation of 1. A 30% reduction in pain corresponds to a mean score of 5.9 and a 10% reduction of pain corresponds to a mean score of 7.7. The sample size analysis is based on a two-sample, two-sided t-test with a significance level of 0.05 and 80% power. The sample size analysis indicates that for a 30% reduction in pain, a total sample size of 46 is required to provide 80% power for the study. To reduce the impact of attrition on the final study results, we plan on recruiting 10% more than the minimum sample size. This amounts to a total of 52 patients (26 patients per arm).

ADVERSE EVENTS AND DATA SAFETY MONITOR

Patients are asked to record any side effects, adverse effects and unanticipated problems daily. In Version 6 Aug 2015

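### Primary pain analysis: baseline adjustment is left to an optional regression prompted by observed imbalance; one baseline-adjusted ANCOVA should be pre-specified instead

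*Combined protocol and SAP*

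**What the plan says.** Study Aim Analysis, item 1, sets the primary comparison: "Change in pain score from baseline to 12 weeks will be compared using a two-sample t-test". The next sentence reads: "A multivariable linear regression model may be considered if baseline differences between groups are observed". Nothing else in the document names the covariates of that regression, says what counts as a baseline difference, or gives its status beside the t-test. The longitudinal models mentioned after the numbered aims are optional and meant to explore the timing of benefit, so they do not settle the primary model.

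Power Analysis sizes the trial on the t-test: "The sample size analysis is based on a two-sample, two-sided t-test with a significance level of 0.05 and 80% power". Its inputs are "We assign the mean baseline pain value of 8.5 to each group with a standard deviation of 1" and "A 30% reduction in pain corresponds to a mean score of 5.9 and a 10% reduction of pain corresponds to a mean score of 7.7", with the result that "a total sample size of 46 is required to provide 80% power for the study". No SD of change and no correlation between baseline and week 12 is given.

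Two neighbouring points affect any adjusted model.
- The Randomization section says "we will stratify subjects based on presence or absence of levator spasm", while Study Design says "Randomization is based on age, diagnosis, and duration of symptoms". None of these factors is carried into the primary analysis.
- The Primary goal hypothesis names both the visual analog scale and the Brief Pain Inventory. Study Design lists only the visual analog scale for pain, and item 1 does not say which score it means.

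**The concern.** A change score does not remove baseline imbalance unless the regression slope of week-12 pain on baseline pain is 1. If the slope is below 1, the arm that starts with more pain tends to show a larger fall through regression to the mean. If it is above 1, the bias runs the other way. Over all randomisations this averages out, so the t-test keeps its 5%. In a particular trial with a visible baseline difference it need not, and that is when the plan opens a second model without defining it.

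Two things are then at stake. The fixed test may mislead in the very trial where imbalance is seen, and a second analysis can be shaped after the data are known. With 26 women per arm and a planned baseline mean of 8.5 on a 10-point scale, both chance imbalance and regression to the mean are realistic.

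**Working it through.** **Inputs.** From Power Analysis: 46 women analysed (23 per arm), two-sided 5%, 80% power, baseline mean 8.5 and SD 1, reductions of 30% and 10%. The difference is 0.30 × 8.5 − 0.10 × 8.5 = 1.7 (1.8 from the rounded means 5.9 and 7.7). Assumed, because not given: correlation ρ = 0.2, 0.3, 0.5 or 0.7, and normal scores.

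**The plan's own figure.** A difference of 1.8 with SD 1 needs 6 per arm by the exact t-test, or 12 in total, so 46 does not follow from the stated inputs. That is a separate matter. Here it means the SD of change has to be inferred. Solving the noncentral t (44 df, 23 per arm) for 80% power gives a standardised difference of 0.845, so the change SD is 1.7/0.845 = 2.01 (2.13 for 1.8). This is not the only explanation: a difference of 0.85 with SD 1 also gives 23 per arm.

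**Week-12 SD implied.** With s0 = 1 at baseline and change SD 2.01, s1 = ρ + √(ρ² + 2.01² − 1) = 1.96, 2.07, 2.32, 2.58. The slope β = ρ·s1/s0 is 0.39, 0.62, 1.16, 1.81.

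**Why imbalance matters.** Given a baseline difference D, the null expectation of the difference in change is (β − 1)·D, while ANCOVA subtracts β·D. At SD 1, baseline pain differs at p<0.05 once D reaches 2.015 × √(2/23) = 0.59. The standard error of the change difference is 2.01 × √(2/23) = 0.59. At that threshold the bias is −0.36 points (0.6 SE) for β = 0.39, and +0.48 points (0.8 SE) for β = 1.81.

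**Null rejection given baseline p<0.05** (at least 100,000 simulated null trials per setting; repeat runs differ by up to about one percentage point):

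| SDs (baseline, week 12) | ρ 0.2 | 0.3 | 0.5 | 0.7 |
|---|---|---|---|---|
| t-test, 1 and implied s1 | 9% | 7% | 5% | 13% |
| t-test, 1 and 2 | 9% | 7% | 5% | 9% |
| t-test, equal | 27% | 24% | 18% | 13% |
| ANCOVA, all settings | about 5% | about 5% | about 5% | about 5% |

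With equal SDs nearly all these t-test rejections favour the arm that began with more pain. With unequal SDs and ρ = 0.7 the direction reverses. Where β is 1 (SDs 1 and 2, ρ = 0.5) there is no excess.

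**Overall type I error.**
- t-test alone 4.9% to 5.1%; ANCOVA alone 5.0% to 5.1%.
- Smaller p-value allowed only after imbalance: 5.0% to 5.2% (trigger p<0.05), 5.2% to 5.5% (trigger p<0.20).
- ANCOVA strictly replacing the t-test after baseline p<0.05: 3.9% to 5.0%.
- Free choice between the two tests: 6.8% to 8.0% with equal SDs.

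Choosing covariates after seeing the data was not simulated.

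**Power at a difference of 1.7.** With k covariate degrees of freedom and no prognostic value beyond baseline pain, the residual variance is s1²(1 − ρ²)(1 + k/(43 − k)) on 44 − k df. The t-test has 80.0%.

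| Model | ρ 0.2 | 0.3 | 0.5 | 0.7 |
|---|---|---|---|---|
| Baseline pain (k=1) | 82.7% | 80.4% | 79.3% | 85.6% |
| + one binary stratum (k=2) | 81.8% | 79.5% | 78.3% | 84.7% |
| + three single-df factors (k=4) | 79.8% | 77.4% | 76.1% | 82.8% |
| + five extra df (k=6) | 77.5% | 75.1% | 73.8% | 80.7% |

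The worst losses, all at ρ = 0.5, are 0.7, 1.7, 3.9 and 6.2 points. With SD 1 at both visits, power for 1.7 exceeds 99% either way.

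**The case against.** The strongest reply is that the primary test is settled: item 1 commits to the t-test, the sample size rests on it, and the regression is only optional. On the natural reading it is a supplement, and one clause naming its covariates and calling it supportive would remove the ambiguity. That the t-test is fixed stands. A reader might infer that the plan has no primary test or leaves a free choice between two; the wording does not support this. What remains open is the weight of the regression if the two disagree.

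A second reply is that the harm is small and depends on assumptions. This also stands in part. The larger conditional figures need equal SDs, which sit badly with the SD implied by 46 women. Under the implied SDs the excess runs from none to about 8 points and changes direction with ρ. A reader might also infer a type I error of 7% to 8%, but that needs an unrestricted choice the plan does not offer. Nor can a large power gain be claimed: the implied SD is only one explanation of the sample size, and under it the change is small.

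None of this defends observed imbalance as the rule for adjusting.

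**Conclusion.** The concern holds in a limited form and should be acted on. The planned t-test is fixed and valid overall, but it ignores baseline pain, and the only provision for adjustment is undefined and depends on what the data show. In null trials with a significant difference in baseline pain (1 in 20), the t-test's error is about 5% to 13% under the SDs implied by the sample size and about 12% to 27% with equal SDs, against about 5% for ANCOVA. These figures assume 23 per arm, normal scores and ρ from 0.2 to 0.7. The 1-in-20 frequency is for p<0.05 on baseline pain alone; the plan sets no threshold and does not confine its trigger to that variable.

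The case rests on holding the error rate when imbalance occurs and on removing a data-dependent decision. It does not rest on overall type I error or on power.

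**What to change.** Replace item 1 with one pre-specified primary analysis: ANCOVA of the week-12 score, on a single named primary pain scale, with arm and baseline pain as terms. Delete the sentence that ties adjustment to observed baseline differences, and keep the change-score t-test as a labelled sensitivity analysis. Reconcile the Study Design and Randomization sections to one scheme, then add the stratification factor actually used.

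The cost is a few sentences of analysis text, with no new data, visits or patients. In the settings tried, the worst power loss is about 0.7 points with baseline pain alone and about 1.7 points with one unprognostic binary stratum. It reaches about 4 to 6 points if three to five extra degrees of freedom are spent on unprognostic factors or a multi-level one. Prognostic factors would offset this, but with 46 women the covariate set should stay small.

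### The SF-36 and FSFI comparisons use baseline only by subtraction, omit the stratification factor and plan no effect estimate; a baseline-adjusted analysis would generally be more precise

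*Combined protocol and SAP*

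**What the plan says.** Under Study Aim Analysis, item 2 reads "Changes in SF-36 subscores from baseline to 12 weeks will be compared using Wilcoxon rank sum tests". Item 3 gives the sexual-function scale the same treatment: "Changes in FSFI subscales from baseline to 12 weeks will be compared using Wilcoxon rank" sum tests. Neither item names a covariate, a stratum, an effect measure or a confidence interval.

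The Randomization section says "we will stratify subjects based on presence or absence of levator spasm". The Study Design section describes the allocation differently: "Randomization is based on age, diagnosis, and duration of symptoms". No item in Study Aim Analysis uses any of these factors. Study Design has quality of life and sexual function assessed at baseline and at 4, 8 and 12 weeks, so the baseline value of each subscale will be available.

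Adjustment appears in two other places:

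- Item 1, on pain: "A multivariable linear regression model may be considered if baseline differences between groups are observed". This is optional, depends on the observed data, and is not extended to items 2 and 3.
- The closing text of Study Aim Analysis, where mixed models "may be used in subsequent analyses to explore the length of time that elapses before the treatment benefit is observed". These are optional and exploratory, and no covariates are named.

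**The concern.** Subtracting baseline fixes its coefficient at 1. If the true slope of week-12 score on baseline is not 1, the change score is noisier than it needs to be, and part of any chance baseline difference between arms stays in the comparison. In a trial of 52 such differences are not rare. With 23 evaluable per arm, the standard error of a baseline difference is √(2/23) = 0.29 SD, so an imbalance of 0.3 SD or more is expected in about 31% of trials. With equal SDs, the change score carries (1 − ρ) times that imbalance into the result.

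The second loss is in reporting. Quality of life and sexual function are two of the three secondary goals, and the Significance section looks ahead to a larger multi-center trial. Planning that trial needs effect sizes with intervals, and a rank sum p-value does not supply them.

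**Working it through.** **Inputs from the documents.** 46 evaluable (23 per arm) and 52 recruited (26 per arm), from Power Analysis; two-sided 0.05. The plan gives no power, SD, effect size or correlation for SF-36 or FSFI, so there is no figure of its own to reproduce on this point. The only sample-size calculation is for pain. (That one does not reproduce: means of 7.7 and 5.9 with SD 1 need 12 in total, not 46. This is a separate matter, and only the arm sizes are used here.)

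**Assumed inputs.** Within-arm correlation ρ between baseline and week 12 of 0.3, 0.5 and 0.7; ratio k of the week-12 SD to the baseline SD.

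**Step 1, formulas.** With baseline SD set to 1, the variance of the treatment contrast is proportional to

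- change score: 1 + k² − 2ρk
- baseline-adjusted (ANCOVA): k²(1 − ρ²)

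The proportion saved is (1 − ρk)² / (1 + k² − 2ρk). It is never negative in large samples and is zero when the slope ρk equals 1. With k = 1 it reduces to (1 − ρ)/2.

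**Step 2, equal SDs (k = 1).**

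| ρ | Variance ratio (1+ρ)/2 | Variance saved | Standard error saved, 1 − √ratio |
|---|---|---|---|
| 0.3 | 0.65 | 35% | 19% |
| 0.5 | 0.75 | 25% | 13% |
| 0.7 | 0.85 | 15% | 8% |

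Over ρ from 0.1 to 0.9 the variance saving runs from 45% down to 5%. Estimating the slope costs a factor of about 1 + 1/(N − 4). At N = 52 this is 1.021, and the savings become 33.6%, 23.4% and 13.2%.

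**Step 3, unequal SDs.** For example, at k = 1.25 and ρ = 0.5: adjusted 1.5625 × 0.75 = 1.172; change 1 + 1.5625 − 1.25 = 1.3125; ratio 0.893; saving 11%.

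| k | ρ = 0.3 | ρ = 0.5 | ρ = 0.7 |
|---|---|---|---|
| 0.8 | 50% | 43% | 37% |
| 1.0 | 35% | 25% | 15% |
| 1.25 | 22% | 11% | 2% |
| 1.5 | 13% | 4% | 0.2% |

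**Step 4, power.** At 23 per arm, an effect with 60% power under a t-test on change scores has 78%, 72% and 67% under ANCOVA for ρ = 0.3, 0.5 and 0.7 with k = 1 (noncentral t, before the slope cost of about one point). With k = 1.5 these become 66%, 62% and 60%.

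**Step 5, the test actually planned.** Steps 1 to 4 use a t-test on change as comparator. A simulation of the Wilcoxon test on change against ANCOVA (normal data, equal SDs, 26 per arm, assumed difference of 0.7 SD) gave power of 0.53 vs 0.73, 0.66 vs 0.80 and 0.87 vs 0.93 for ρ = 0.3, 0.5 and 0.7. With no treatment effect and no stratum effect (ρ = 0.5), the Wilcoxon test rejected in 5.0% of runs.

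**Step 6, the stratum.** Adding a stratum with no prognostic effect gave no gain. With an assumed stratum effect of 0.6 SD, it raised ANCOVA power by about 3 to 4 points (for example 0.77 to 0.81 at ρ = 0.5).

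**The case against.** The strongest reply is that the planned analysis is sound. A rank sum test on change is valid under randomisation, suits bounded and possibly skewed subscales, and uses baseline through the subtraction. The endpoints are secondary, and the sample size rests on pain. That all stands, and it keeps this a matter of efficiency and estimation.

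The size of the gain is also uncertain. It depends on ρ and on the SD ratio, and the documents give neither. Study Design requires functional disability at entry, which could narrow the baseline spread and push k above 1, where moderate values shrink the saving almost to nothing. If changes are skewed or heavy-tailed, the normal-theory ratio does not describe the loss. This stands too.

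Four stronger readings are therefore not supported:

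- *The tests ignore baseline.* They subtract it; what is missing is adjustment for it.
- *The trial loses 15% to 35% of its precision.* That is a variance figure under assumed ρ and equal SDs, not a property of this trial.
- *Omitting levator spasm contributes to that figure.* The figure comes from baseline adjustment alone, and any gain from the stratum depends on how prognostic it is.
- *The results would be biased.* Nothing in the plan implies this.

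What does not stand is the suggestion that other text already supplies the adjustment. The regression belongs to the pain item and is conditional; the mixed models are optional, exploratory and without stated covariates.

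**Conclusion.** The point holds as one of precision and reporting on secondary endpoints. Items 2 and 3 plan valid but unadjusted tests, although the baseline scores will be collected and the allocation is said to be stratified, and they plan no effect estimate with an interval. Baseline adjustment is generally more precise. Against a t-test on change, the variance saving is 35%, 25% or 15% for assumed correlations of 0.3, 0.5 or 0.7 with equal SDs. It ranges from 50%, 43% and 37% at an SD ratio of 0.8 to 22%, 11% and 2% at 1.25. The lack of a planned treatment difference and confidence interval does not depend on any of these assumptions. The change is worth making because it needs no new data; leaving the plan as it is would not invalidate the trial.

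**What to change.** 1. Reconcile Study Design (age, diagnosis, duration of symptoms) with Randomization (levator spasm), and state which factor or factors the allocation actually uses.
2. For each SF-36 and FSFI subscale, pre-specify a linear model of the week-12 score on arm, baseline score and the actual stratification factor. Report the adjusted difference with its 95% CI.
3. Decide in advance whether the model is linear, rank-based or proportional-odds, and not after seeing residuals by arm. If it is not linear, name the effect measure that will be reported.
4. Keep the Wilcoxon test on change as a sensitivity analysis.

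The cost is SAP wording, a degree of freedom for each added term, and a little more analysis work. No additional data or visits are needed.

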InControl Medical created a line of products FDA approved for urinary incontinence and fecal incontinence (10). These devices are non-implanted, customizable, battery-operated vaginal probes made of medical grade silicon and provide electrical stimulation to the pelvic floor. One of the devices, ApexMTM provides electrical stimulation at frequencies alternating between 13 Hz and 50 Hz and allows the clinician to adjust the intensity as well as the duration of the electrical stimulation. We propose the use of low power electrical stimulation for the treatment of pain in patients diagnosed with CPP. We will deliver the electrical stimulation using ApexMTM, adjusting the power to a sensory threshold to prevent muscle contraction.

Primary goal:

To evaluate the use of a domiciliary intravaginal, non- implanted electrical stimulation device in the treatment of chronic pelvic pain. Hypothesis: ES will decrease pain as measured by the visual analog scale and brief pain inventory (18).

Secondary goals:

To evaluate the effect of ES on overall quality of life. Hypothesis: ES will improve quality of life as measured by the Short Form-36. (16)

To evaluate the effect of ES on sexual function. Hypothesis: ES will improve sexual functioning as measured by Female Sexual Function Index (17)

To evaluate the use of ES on use of pain medications. Hypothesis: ES will decrease dosage and frequency of pain medication use. This will be measured by use of a daily pain medication journal. Patients will complete a journal listing the type, amount and dosage of pain medications used on a daily basis.

SIGNIFICANCE

If a positive effect is seen, a personal vaginal device designed for home use can be offered to patients with chronic pelvic pain. Patients would be able to take pelvic floor rehabilitation from the physical therapy office into their home. Furthermore, it would justify a larger, multi-center, randomized Version 6 Aug 2015

controlled trial comparing the ApexMTM device to standard in office physical therapy.

STUDY DESIGN

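### Item 4 names Poisson regression for medication frequency but states no variance method; with ordinary Poisson errors on follow-up counts, the 5% test is miscalibrated whenever variance and mean differ

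*Combined protocol and SAP*

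**What the plan says.** The medication goal under Secondary goals is that stimulation will lower both the dosage and the frequency of pain medication. The source is the journal: "Patients will complete a journal listing the type, amount and dosage of pain medications used on a daily basis".

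Item 4 of STUDY AIM ANALYSIS splits this into two comparisons. Dose gets a Wilcoxon rank sum test. For frequency the text is "Frequency of medication from baseline to 12 weeks may be compared using a poison regression model" (Poisson is meant). It does not say whether frequency is a number of doses or a number of days with use.

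Three other statements bear on the point:

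- STATISTICAL METHODS allows univariable comparisons by t-tests, "Wilcoxon rank sum tests, or Chi-square tests, depending on the level of measurement and data distributions".
- The paragraph after item 4 sets the threshold: "In all analyses, statistical significance will be determined by a p-value less than or equal to 0.05".
- The same paragraph names linear and generalized linear mixed effects models, which "may be used in subsequent analyses to explore the length of time that elapses before the treatment benefit is observed".

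Overdispersion, quasi-Poisson, negative binomial, robust errors and an offset are mentioned nowhere.

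**The concern.** Ordinary Poisson regression takes the variance of each woman's count to equal its mean. Analgesic counts have no reason to obey this. If women differ in how often they take medication, the spread of totals exceeds the mean, the model's standard error is too small, and chance differences between arms pass p ≤ 0.05 too often. If the count is capped, as days of use are, or if nearly everyone follows a fixed routine, the spread can be below the mean and the test loses power. At stake is a reported effect on medication frequency that is really noise, or a real effect that is missed. The primary pain comparison and the dose comparison are untouched.

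**Working it through.** **Inputs.** From the documents: 12 weeks of follow-up (12 × 7 = 84 days); 46 patients before the attrition allowance, so 23 per arm (POWER ANALYSIS, where the number is derived for pain only); a two-sided 5% level. The documents give no figure for item 4 to reproduce and no usage data. Mean use, between-woman CV and within-woman correlation (ICC) below are therefore assumptions, shown as a range.

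**Size of the test.** Compare follow-up counts by arm alone, N per arm, mean count μ, and let φ = variance/mean. The Poisson variance of the log rate ratio is 2/(Nμ), while the true variance is about 2φ/(Nμ). The test statistic then has standard deviation √φ, so

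actual size = 2 × [1 − Φ(1.96/√φ)].

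N cancels, so recruiting more patients does not cure the problem.

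**Dose counts.** If women's rates vary (gamma) and each woman's count is Poisson, φ = 1 + μ × CV².

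| Assumed use over 84 days | φ | Size, ordinary Poisson |
|---|---|---|
| 0.25/day, CV 0.3 (μ = 21) | 1 + 21 × 0.09 = 2.89 | 25% |
| 1/day, CV 0.1 (μ = 84) | 1 + 84 × 0.01 = 1.84 | 15% |
| 1/day, CV 0.5 (μ = 84) | 1 + 84 × 0.25 = 22 | 68% |
| 2/day, CV 1.0 (μ = 168) | 1 + 168 × 1 = 169 | 88% |

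The reverse case: one dose a day with 5% missed at random gives φ = 1 − 0.95 = 0.05 and a size of practically 0%. At a mean of 84, φ passes 1 once women's totals have a CV above 1/√84 = 10.9%.

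**Days of use.** With a share p of days with use and correlation ICC (beta-binomial), φ = (1 − p) × (1 + 83 × ICC).

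| p, ICC | φ | Size, ordinary Poisson |
|---|---|---|
| 90%, 0.05 | 0.1 × 5.15 = 0.515 | 0.6% |
| 80%, 0.02 | 0.2 × 2.66 = 0.532 | 0.7% |
| 90%, 0.1 | 0.1 × 9.3 = 0.93 | 4.2% |
| 80%, 0.1 | 0.2 × 9.3 = 1.86 | 15% |
| 50%, 0.1 | 0.5 × 9.3 = 4.65 | 36% |
| 50%, 0.3 | 0.5 × 25.9 = 12.95 | 59% |

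The second row shows that conservatism is not confined to near-daily use.

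**Simulation.** With 20,000 null trials per scenario at 23 per arm, ordinary Poisson sizes agree with both tables to within about one percentage point. With a Pearson dispersion and a t reference on 44 degrees of freedom, size is about 4.5% to 5.3% in these scenarios. Near the ceiling the repair is itself conservative: about 2.4% at 97% of days with ICC 0.3.

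**If a within-woman change is meant.** Assume a 28-day baseline count (mean m₀), an 84-day follow-up count (mean m₁) and an arm-by-period comparison. Stable individual rates cancel and size is about 5%. If each woman's rate drifts between periods with CV d, φ ≈ 1 + d²(1 + CV²)/(1/m₀ + 1/m₁).

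- 1/day, CV 0.5, d = 0.15: 1 + 0.0225 × 1.25/0.0476 = 1.59, about 12%.
- 2/day, CV 1.0, d = 0.3: 1 + 0.09 × 2/0.0238 = 8.56, about 50% by formula and 48% to 49% by simulation.

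**The case against.** The strongest reply is that this is an omission and not an error. Item 4 says that frequency may be compared this way, where items 1 to 3 and the dose sentence say will. No variance estimator is fixed, a rank test is available under STATISTICAL METHODS, and an experienced analyst would look at the dispersion. All of that is true, and it limits the weight of the point. It does not remove it. Nothing says when a rank test would replace the Poisson model, so methods with very different error rates stay open until the data are seen. The mixed models could represent differences between women, but they are optional and concern the timing of benefit.

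A reader might infer that the plan prescribes ordinary Poisson errors, or that this trial faces a false-positive rate of 68% or 88%. The documents support neither. They leave the variance open and contain no usage data, and those rates belong to an arm-only comparison of follow-up counts under assumed variation. Items 1 to 3 analyse changes, and item 4's period wording could mean the same; the result is then near 5% if individual rates are stable. Nor is the test always too liberal for dose counts: that needs women to differ in their rate of use, and uniform regular dosing reverses it.

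**Conclusion.** The point holds in conditional form. Item 4's only named model for frequency comes without any provision for dispersion. On its plain reading (variance equal to mean, follow-up counts, arm-only comparison), the 5% test is calibrated only where φ happens to be near 1. For dose counts modest differences between women suffice to inflate it: 15% at CV 0.1 with an assumed 1 dose a day. For days of use the direction cannot be known beforehand. The direction and the formulas are secure; the sizes are sensitivity figures that rest on assumed use. It is a minor point, confined to one component of one of three secondary goals, but it has a specific and inexpensive remedy.

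**What to change.** Replace the frequency sentence of item 4 with wording such as:

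*Frequency is the number of [doses of pain medication / days with any pain medication: state one] recorded in the daily journal from baseline to 12 weeks. Arms will be compared by Poisson regression with a log link, standard errors scaled by the estimated Pearson dispersion (quasi-Poisson, t reference), and log(completed journal days) as offset.*

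If days are chosen, a binomial-type model with an estimated dispersion is an alternative, because quasi-Poisson is conservative near the ceiling. A negative binomial Wald test is not an equal substitute at this sample size: simulated size for dose counts was 6.2% to 7.2%. If a change from baseline is meant, item 4 must say so and say how the baseline count is obtained; a change can be negative and cannot be the response in a Poisson model.

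**Cost.** One sentence, after the team has decided what is counted, and no new data if the count can be read from the journal. Intervals for dose counts will usually be wider, by a factor of about √φ: 1.7, 4.7 and 13 for φ = 2.89, 22 and 169. Power is correspondingly lower than ordinary Poisson errors would suggest. For a 30% lower dose rate that starts at once, power at 23 per arm over 84 days is about 87%, 63% and 21% in those three scenarios. That is a cost of honest errors and not of the method.

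The choice of count window, and the differing descriptions of the randomization factors in STUDY DESIGN and RANDOMIZATION, are separate matters and not part of this change.
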